2.1 Objectives and Endpoints

Objectives	Endpoints
Primary	

 • To evaluate the efficacy of talimogene laherparepvec in combination with pembrolizumab as assessed by objective response rate (ORR) in subjects with unresectable/metastatic stage IIIB-IVM1d melanoma who have progressed on prior anti-PD-1 therapy 	
 • Overall response (complete response [CR]+partial response [PR]) (by investigator assessment using modified RECIST v1.1)
Key Secondary	

 • To evaluate the efficacy of talimogene laherparepvec in combination with pembrolizumab, as assessed by: 
 ○ Complete response rate (CRR), best overall response (BOR), durable response rate (DRR), duration of response (DOR), and disease control rate (DCR) ○ ORR using modified irRC-RECIST ○ Progression free survival (PFS) ○ Overall survival (OS) 	
 • Complete response, BOR, durable response, DOR and disease control, (investigator assessment using modified RECIST 1.1 and modified irRC-RECIST) and overall response using modified irRC-RECIST by investigator assessment • PFS (by investigator assessment using modified RECIST 1.1 and modified irRC-RECIST) • OS

 • To evaluate the safety of talimogene laherparepvec in combination with pembrolizumab as assessed by incidence of treatment-emergent and treatment-related adverse events, and abnormal laboratory tests in patients who have progressed on prior anti-PD-1 therapy 	
 • Incidence of treatment-emergent and treatment-related adverse events (all adverse events, grade ≥ 3 adverse events, serious adverse events, fatal adverse events, adverse events defined as events of interest), and abnormal laboratory tests

• To evaluate time to subsequent anticancer therapy	
• Time to subsequent anticancer therapy
---	---

Exploratory	
	

2.2 Hypotheses and/or Estimations

No formal hypothesis testing will be performed. All analyses will be descriptive in nature.

3. Study Overview

3.1 Study Design

This is a phase 2, open-label, single-arm, multicenter clinical trial designed to evaluate the efficacy and safety of talimogene laherparepvec in combination with pembrolizumab following disease progression on prior anti-PD-1 therapy in unresectable/metastatic melanoma (stage IIIB-IVM1d) or prior anti-PD-1 therapy in the adjuvant setting.

Subject must have received prior anti-PD-1 therapy for at least 2 to 3 consecutive cycles within an 8-week period (based on administration schedule) and have disease progression as defined by RECIST 1.1 criteria. The initial evidence of disease progression must have been confirmed by a second assessment no less than 4 weeks from the first documented disease progression, in the absence of rapid clinical progression. The anti-PD-1 therapy must be the immediate prior line of therapy before enrollment and subjects with disease progression on more than 1 line of anti-PD-1 therapy are not eligible.

Subjects will be enrolled into 1 of 4 cohorts based on prior anti-PD-1 experience:

- **Cohort 1 – Locally Recurrent/Metastatic - Primary Resistance**

Subjects who received anti-PD1 therapy in the locally recurrent/metastatic setting and experienced a best overall response of disease progression or stable disease prior to confirmed disease progression. The initial date of disease progression must be within 12 weeks of the last dose of a PD-1 inhibitor.

- **Cohort 2 – Locally Recurrent/Metastatic - Acquired Resistance**

Subjects who received anti-PD-1 therapy in the locally recurrent/metastatic setting and experienced confirmed disease progression following a complete or partial response on anti-PD-1 therapy. The disease progression must occur within 12 weeks of the last dose of a PD-1 inhibitor.

- **Cohort 3 – Adjuvant Setting – Disease Free Interval < 6 months**

Subjects who received anti-PD-1 therapy in the adjuvant setting and experienced confirmed disease progression following a disease free interval of < 6 months after starting the adjuvant anti-PD-1 therapy.

- **Cohort 4 – Adjuvant Setting – Disease Free Interval ≥ 6 months**

Subjects who received anti PD-1 therapy in the adjuvant setting and experienced confirmed disease progression following a disease free interval of ≥ 6 months after starting the adjuvant PD-1 inhibitor.

3.2 Sample Size

This is a single-arm estimation study. It is assumed that if the ORR using modified RECIST v1.1 is at least 25%, for this study (N = 100) the lower bound of the 95% confidence interval for an objective response is $> 15\%$.

The 95% CIs for different sample sizes with an assumed ORR of 25% are presented below:

Subjects Enrolled N	Assumed ORR N (%)	95% CI %	Width %
15	4 (26.7)	7.8, 55.1	47.3
30	8 (26.7)	12.3, 45.9	33.6
40	10 (25)	12.7, 41.2	28.5
70	18 (25.7)	16.0, 37.6	21.6
72	18 (25.0)	15.5, 36.6	21.0
100	25 (25)	16.9, 34.7	17.8

Actual number of subjects enrolled in the study: a total of 72 subjects were enrolled in the study (instead of N = 100 subjects planned at the beginning of the study). Twenty-seven subjects were enrolled into cohort 1 and 15 subjects were enrolled into cohorts 2, 3, and 4.

3.3 Adaptive Design

Futility analyses are planned for each of cohorts 1 and 2, separately. The futility criteria are detailed in [Section 7.1](#).

4. Covariates and Subgroups

4.1 Planned Covariates

No covariate analyses will be performed.

4.2 Subgroups

Efficacy analyses on ORR and DCR will be repeated within the following subgroups, overall with cohorts pooled and separately for each cohort:

- Sex (female, male)
- Age at enrolment (<50, ≥50; < 65, ≥ 65; < 75, ≥ 75 years)
- Region (Europe, Non-Europe)
- PD-L1 status (positive, negative, missing/unknown) at baseline
- Disease stage (stage IVM1a or lower, stage IVM1b/c/d) at baseline
- Disease stage (stage IVM1b or lower, stage IVM1c/d) at baseline
- *BRAF*^{V600} mutation at baseline (yes, no)
- LDH (≤ ULN, > ULN; ≤ 2 x ULN, > 2 x ULN)
- ECOG PS (0, 1)
- HSV-1 serostatus at baseline (positive, negative, missing/unknown)
- In-transit disease at baseline (yes, no)
- Prior PD-1 therapy (nivolumab, ipilimumab/nivolumab, pembrolizumab, other)
- Prior anti-cancer therapy and line of therapy for current malignancy
- Prior surgery for current malignancy
- Prior radiotherapy for current malignancy

5. Definitions

• Baseline

Baseline in general refers to study day 1. The baseline value of a parameter (eg, vital signs, laboratory tests, and tumor measurement) is considered to be the latest value prior to receiving any study drug (i.e., on or prior to the first date of dosing). Parameters that are obtained on the same day as the first date of dosing are assumed to be pre-dose if the exact time of the baseline parameter relative to the first dose of any study drug is unknown. For subjects who are not dosed, the baseline value of a parameter is considered to be the latest value prior to the enrollment date. *BRAF* mutational status, which is not sensitive to treatment, will be considered baseline regardless of the timing of ascertainment.

• Best overall response (iBOR) per modified irRC-RECIST

iBOR of complete response (iCR), partial response (iPR), stable disease (iSD), progressive disease (iPD) or unevaluable (iUE) will be derived per modified irRC-RECIST based on investigator assessment. Overall visit response assessments occurring after the start of the first subsequent anticancer therapy will not be included. With the exception of a PD observation, overall visit response assessments occurring on or after a complete or

partial removal/reduction of any target lesion which contained melanoma on pathology evaluation or pathology results were unknown will not be included. The timepoint responses after initial confirmed iPD will not be used to derive BOR. Confirmation of iCR, iPR, and iPD is required as noted in the individual definitions for iCR, iPR and iPD per modified irRC-RECIST (refer to protocol Appendix 10). For the derivation of iBOR, the overall visit response will be considered iSD if it is an unconfirmed iCR or iPR, and iUE if it is either iSD earlier than 77 days after the date of first dose or an unconfirmed iPD when confirmation of iPD is required (ie, initial iPD without clinical instability). As indicated in [Table 5.1](#), iBOR is defined as the best overall visit response in the following order: iCR, iPR, iSD, iPD, or iUE.

Table 5.1 Matrix of Determining iBOR per Modified irRC-RECIST

Visit Overall Response Sequence	Examples	Best Overall Response	Specifications
*, iCR, iCR, *	iPR, iCR, iCR iCR, iCR, iPD	iCR	A confirmatory iCR must be at least 4 weeks (28 days) later; a subsequent iCR within 28 days will not be valid for confirmation and will be ignored; the iCR will also not be confirmed if there is a subsequent iPR/iSD/iPD at any time prior to the next iCR.
*, iPR, iPR, * *, iPR, iCR/iPR, non-iCR, *	iPR, iPR, iPD iPR, iCR, iPD iCR, iPR, iPD	iPR	Criteria for iBOR=iCR not met. A confirmatory iPR/iCR must be no less than 4 weeks (28 days) later; a subsequent iPR/iCR within 28 days will not be valid for confirmation and will be ignored; the iPR will also not be confirmed if there is a subsequent iSD/iPD at any time prior to the next iPR/iCR.
*, iSD, * *, iCR, non- iPR/iCR, * *, iPR, non-iPR/iCR, *	iCR iPD, iCR iPR iPD, iPR, iSD iSD iPD, iSD, iPD	iSD	Criteria for iBOR=iCR or iPR not met. iSD must be ≥ 77 days from date of first dose; however, this is not required for an unconfirmed iCR/iPR.

*,iPD, iPD, * *, iPDci, *
	
iPD, iPD iPD, iSD, iPD, iPD iPD, iUE, iPD iPDci
	
iPD
	
Criteria for iBOR= iCR, iPR, or iSD not met. A consecutive confirmatory iPD must be no less than 4 weeks (28 days) later unless the initial progression qualified for iPDci.; iPDci = the last available iPD “Nonconfirmed Disease Progression with Clinical Instability” as the reason for ending radiographic follow-up.


*, iSD, * iPD
	
iSD iUE, iSD iPD iUE, iPD
	
iUE
	
Criteria for iBOR=iCR, iPR, iSD, or iPD not met. iSD must be < 77 days from date of first dose.

- **Best overall response (BOR) per modified RECIST 1.1**

BORs will be derived based on investigator assessment using modified RECIST 1.1 ([Eisenhauer et al. 2009](#)). Per RECIST 1.1, a confirmation of CR or PR by a consecutive subsequent tumor assessment will not be required for the derivation of BOR. Overall visit response assessments occurring after the start of the first subsequent anticancer therapy will not be included. With the exception of a PD observation, overall visit response assessments occurring on or after a complete or partial removal/reduction of any target lesion which contained melanoma on pathology evaluation or pathology results were unknown will not be included. The timepoint responses after initial PD will not be used to derive BOR. For the derivation of BOR, the overall visit response will be considered UE if it is SD earlier than 77 days after the date of first dose. BOR is defined as the best overall visit response up to and including the first overall visit response of PD in the following order: CR, PR, SD, PD or UE.

- **Complete response rate (iCRR) per modified irRC-RECIST**

Complete response rate (iCRR) per modified irRC-RECIST is defined as the incidence of an iBOR of iCR per modified irRC-RECIST.

- **Complete response rate (CRR) per modified RECIST 1.1**

Complete response rate (CRR) per modified RECIST 1.1 is defined as the incidence of a BOR of CR per modified RECIST 1.1.

- **Disease control rate (iDCR) per modified irRC-RECIST**

Disease control rate (iDCR) per modified irRC-RECIST is defined as the incidence of an iBOR of iCR, iPR or iSD.

- **Disease control rate (DCR) per modified RECIST 1.1**

Disease control rate (DCR) per modified RECIST 1.1 is defined as the incidence of a BOR of CR, PR or SD.

- **Duration of response (iDOR) per modified irRC-RECIST**

Duration of response (iDOR) is defined as the time from the date of an initial response that is subsequently confirmed to the earlier of iPD (see definition of iBOR per modified irRC-RECIST) or death. Subjects who have not ended their response at the time of analysis will be censored at their last evaluable tumor assessment before the start of the first subsequent anticancer therapy.

- **Duration of response (DOR) per modified RECIST 1.1**

Duration of response (DOR) is defined as the time from the date of an initial response of CR or PR to the earlier of PD (see definition of BOR per modified RECIST 1.1) or death. Subjects who have not ended their response at the time of analysis will be censored at their last evaluable tumor assessment date before start of the first subsequent anticancer therapy.

- **Durable response rate (iDRR) per modified irRC-RECIST**

iDRR is defined as the percent of subjects with an iCR or iPR per modified irRC-RECIST with an iDOR \geq 6 months. One month will be calculated based on 365.25 days per year.

- **Durable response rate (DRR) per modified RECIST 1.1**

DRR is defined as the percent of subjects with a CR or PR per modified RECIST 1.1 with a DOR \geq 6 months. One month will be calculated based on 365.25 days per year.

- **End of study (trial) date**

The end of study date is defined as the date when the last subject across all sites is assessed or receives an intervention for evaluation in the study (i.e., last subject last visit), following any additional parts in the study (e.g., long-term follow-up), as applicable.

- **Evaluable tumor assessment**

An overall visit response other than unevaluable (UE or iUE).

- **Events of clinical interest pembrolizumab**

Selected non-serious and serious adverse events known as pembrolizumab events of clinical interest (ECI) that occur after the first dose of pembrolizumab through 90 (+7) days after the last dose of pembrolizumab, or 30 (+7) days after initiation of a new anticancer therapy, whichever is earlier must be reported to Amgen within 24 hours.

- **Events of interest (EOI) for talimogene laherparepvec**

EOIs for talimogene laherparepvec are defined in the version-controlled EOI search strategies maintained by Global Regulatory Affairs and Safety (GRAAS) at Amgen for talimogene laherparepvec

[figure not shown]
- **Investigational product (IP)**

[figure not shown]
Investigational product (IP) refers to Amgen IP talimogene laherparepvec and non-Amgen IP pembrolizumab in this study. IP is also referred as study drug or study therapy.

- **Last date known to be alive**

For subjects not known to have died, their last date known to be alive will be determined as the latest date associated with clinic visits before data cutoff date including, for example, but not limited to the following:

1. Survival status: Last subject status date if status of subject is "Alive"
2. End of study date if the subject's primary reason for ending study is not "Lost to follow-up"
3. Any subsequent anti-tumor therapy initialization date
4. AE start or end date
5. Procedure and concomitant medication start/end date
6. Date of lesion assessments
7. Date of herpetic lesion swabbing
8. Visit date of vital signs; physical exam; ECOG; sample collection for local lab and central lab parameters including HSV-1
9. Date of last investigational product administration

- Objective response rate (ORR) per modified RECIST 1.1

ORR is defined as the incidence of a BOR of CR or PR per modified RECIST 1.1. Subjects who do not have any post-baseline tumor assessments will be regarded as non-responders.

- **Objective response rate (iORR) per modified irRC-RECIST**

iORR is defined as the incidence of an iBOR of iCR or iPR per modified irRC-RECIST. Subjects who do not have any post-baseline tumor assessments will be regarded as non-responders.

- **Overall survival (OS)**

Overall survival is defined as the interval from first dose to death from any cause. Subjects without an event will be censored at the last date known to be alive.

- **PD-L1 Status**

PD-L1 expression from tumor biopsy tissue samples will be reported as positive or negative. PD-L1 expression is said to have positive status if the **combined positive score (CPS)** is $\geq 1\%$, and negative status if **CPS** is $<1\%$.

- **Primary completion date**

The primary completion date is defined as the date when the last subject is assessed or receives an intervention for the final collection of data for the primary endpoints for the purpose of conducting the primary analysis, whether the study concluded as planned in the protocol or was terminated early.

The primary completion date is the date when the last subject has completed the assessments for week 24.

- **Progression-free survival (iPFS) per modified irRC-RECIST**

iPFS per modified irRC-RECIST is defined as the interval from first dose to the earlier event of iPD (per modified irRC-RECIST) or death from any cause. Subjects without an event will be censored at their last evaluable post-baseline tumor assessment if available, otherwise will be censored on study day 1.

- **Progression-free survival (PFS) per modified RECIST 1.1**

PFS per modified RECIST 1.1 is defined as the interval from first dose to the earlier event of PD (per modified RECIST 1.1) or death from any cause. Subjects without an event will be censored at their last evaluable post-baseline tumor assessment if available, otherwise will be censored on study day 1.

- **Safety follow-up visit**

Safety follow-up visit will be performed approximately 30 (+7) days after the last dose of IP. If an end of treatment decision occurs > 30 (+7) days after the last treatment date, then safety follow-up will be performed as soon as possible (eg, within a week of end of treatment decision).

- **Serious adverse event (SAE)**

Serious adverse events (SAE) are defined as any adverse event categorized as serious as determined by investigator per protocol defined criteria.

- **Study day**

Study day is calculated from the first day IP is administered (i.e. non-zero dosing).

If visit date is on or after first dose date then:

$$\text{Study day} = \text{visit date} - \text{first dose date} + 1$$

if visit date is before first dose date then:

$$\text{Study day} = \text{visit date} - \text{first dose date}$$

- **Study week 0**

The start of IP administration (i.e. non-zero dosing) to the subject is study week 0. Study day 1 is corresponding to study week 0.

- **Time to subsequent anticancer therapy**

Time to subsequent anticancer therapy is defined as the time from enrollment to the start of subsequent anticancer therapy. Subjects who have not started subsequent anticancer therapy will be censored on their last visit date.

- **Treatment-emergent adverse events (TEAE)**

Treatment-emergent adverse events are defined as any adverse event occurring after initiation of the first dose of study therapy through 30 days after the last administration of study therapy. Adverse events that occur on the same day as the first dose date of study therapy will be treated as treatment-emergent events unless indicated otherwise (for example, if an event occurs on the same date as the first administration of study therapy and the check box indicating prior to the first dose of study therapy is checked on eCRF, then the event will not be counted as a treatment-emergent AE).

[figure not shown]
- **Treatment-emergent serious adverse events (TESAE)**

Treatment-emergent serious adverse events are defined as any SAE occurring after initiation of the first dose of study therapy through 90 days after the last administration of study therapy or 30 days after the last administration of study therapy if the subject initiates new anti-cancer therapy, whichever is earlier.

SAEs that occur on the same day as the first dose date of study therapy will be treated as treatment-emergent SAEs unless indicated otherwise (for example, if an event occurs on the same date as the first administration of study therapy and the check box indicating prior to the first dose of study therapy is checked on eCRF, then the event will not be counted as a treatment-emergent SAE).

- **Treatment period**

Treatment period is defined as the period between the first date of study therapy administration and 30 days after the last study therapy administration.

6. Analysis Set

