Lesion assessments including radiographic and clinical assessments	X							X					X	Q12W	X	Q12W	Radiographic tumor imaging (CT, PET/CT, or MRI) of the chest, abdomen, and pelvis, and CT or MRI of the brain are required at screening. Tumor assessments must also include all other sites of disease. For subjects who discontinue treatment for any reason other than confirmed iPD per modified irRC-RECIST, every effort should be made to complete radiographic assessments every 12 weeks (±1 week) or more frequently if clinically indicated during the long-term follow-up until documentation of confirmed iPD per modified irRC-RECIST (Section 12.10), clinical progression, start of new anticancer therapy, or end of study, whichever occurs first. Subjects who have reached a confirmed CR may increase their interval of radiographic assessments up to 6 months (26 weeks) after the first 2 years beyond confirmed CR and up to 12 months (52 weeks) after the first 5 years beyond confirmed CR as long as CR is maintained. Radiographic imaging is only required at the safety follow up visit if the subject ended treatment prior to confirmed PD and has not had radiographic tumor imaging performed within 4 weeks (+1 week) of the visit.
Modified RECIST v1.1	X							X					X	Q12W	X	Q12W	Following modified RECIST v1.1 tumor assessments will continue through to PD. See Section 12.10
Modified irRC-RECIST	X							X					X	Q12W	X	Q12W	Following modified irRC-RECIST, tumor assessments will continue until confirmed iPD. See Section 12.10

Footnotes defined on last page of this table

Table 2-1. Schedule of Activities

PROCEDURE	Screening			Treatment Period (Weeks) ^a											Follow-up		Notes
	≤ 28 days	≤ 14 days	≤ 72 hr	0	3	6	9	12	15	18	21	24	>24 ^b	Safety (30 [+7] days post last dose) ^c	Survival ^d		
CLINICAL OUTCOME ASSESSMENTS (CONTINUED)																	
Survival assessment															X	Subjects will be followed for survival every 12 weeks (± 28 days) from the date of the safety follow-up visit (or from the planned visit date if the safety follow-up visit does not occur) until: death, subject withdraws full consent, or up to 36 months after the last subject is enrolled. Assessments will include anticancer therapy, radiation, surgery, disease progression, and serious adverse event reporting as described above and in Sections 9.2.3.1.1.2 and 9.2.3.1.1.3.	

Footnotes defined on last page of this table

Product: Talimogene Laherparepvec (T-VEC)

Protocol Number: 20180115

Date: 09 June 2021

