7.1.5 Other Treatment Procedures

Investigators may choose to resect lesions which become suitable for resection to render the subject free of macroscopic disease. Additionally, biopsies may be taken of cutaneous or subcutaneous lesions for tumor analysis during the study. However, resection of lesions may occur only following tumor assessment. If a subject undergoes resection of the lesion, the investigator or designee should notify the sponsor medical monitor as soon as possible. [REDACTED]

[REDACTED]

Local radiation treatment to the site of bone and other metastasis will be permitted for palliative pain management at any time during the study. If a subject undergoes local radiation, the investigator or designee should notify the sponsor's medical monitor as soon as possible.

If a subject demonstrates evidence of new or worsening central nervous system (CNS) metastases, all study treatments should be withheld and the investigator or designee should notify the sponsor's medical monitor as soon as possible. Subjects may be allowed to remain on study after discussion between the sponsor's medical monitor and the investigator to determine the appropriateness of treatment resumption provided CNS lesions can be treated with stereotactic radiotherapy, Gamma Knife, or craniotomy. After approval is obtained from the sponsor's medical monitor, subjects may be allowed to reinitiate talimogene laherparepvec and/or pembrolizumab treatment per Section 7.4.1, following stereotactic radiotherapy only when dosing of corticosteroid is below 1.5 mg dexamethasone, 10 mg prednisone or equivalent. If higher doses of corticosteroid are used, talimogene laherparepvec and/or pembrolizumab must be held until that dose level is reached during the period of steroid tapering.

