Decrease < 30% to Increase < 20%	Unequivocal progression	Any	iSD
Increase ≥ 20% ^f	Any	Any	iPD ^{b,f}
UE	Any	Any	iUE
ND	Any	Any	iUE
NA ^c	Any	Any	iUE

^a Decreased disease relative to baseline, including new measurable lesions only (≥ 10 mm for non-lymph node lesions, ≥ 15mm in short axis for lymph nodes).

^b iCR, iPR, or iPD should be confirmed by a second, consecutive assessment at least 4 weeks (28 days) apart. Rapid clinical deterioration is an exception for confirming initial PD.

^c No target lesions identified at baseline. When a patient has only non-measurable disease (ie, no target lesions identified at baseline) the response will be unevaluable.

^d No non-target lesions identified at baseline.

^e Disappearance of all non-lymph node lesions and all lymph nodes < 10 mm in short axis would also be iCR even if lymph node measurements prevent 100% tumor burden reduction.

^f In addition to relative increase of > 20%, the tumor burden must also demonstrate an absolute increase of > 5 mm from nadir for iPD. If the tumor burden does not demonstrate > 5 mm increase from nadir but tumor burden is increased > 20% from the nadir, response should be recorded as iSD.

Note: Unequivocal iPD of non-target lesions and/or the appearance of new, non-measurable lesions do not constitute overall iPD.

For subjects who have initial-PD, it is at the discretion of the investigator to continue a subject on study treatment until repeat imaging is obtained a minimum of 4 weeks later. Subjects with a global deterioration of health status requiring discontinuation of treatment without objective evidence of PD at the time are to be classified as “clinically unstable” based on the investigator’s clinical judgement of the subject’s overall clinical condition, including performance status, clinical symptoms, and laboratory data. Clinical instability considers the following criteria based on the investigator’s clinical judgement:

Signs and symptoms indicating PD:

- Decline in ECOG performance status
- Rapid clinical progression of disease
- Progressive tumor at critical anatomical sites (eg, cord compression, clinically active brain metastases, compression of vital organ structures) requiring urgent alternative medical intervention

Amendment 3

Protocol Title: Phase 2 Study of Talimogene Laherparepvec in Combination With Pembrolizumab in Subjects With Unresectable/Metastatic Stage IIIB-IVM1d Melanoma Who Have Progressed on Prior Anti-PD-1 Based Therapy

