9.7 Other Analyses

ECOG performance status scores will be summarized at each time point. Changes in scores for ECOG performance status scores from baseline will also be tabulated.

Spider plots for subject-level percent change from baseline in tumor burden by BOR per modified RECIST 1.1 and iBOR per modified irRC-RECIST and disease stage at baseline will be provided. Waterfall plots for subject-level maximum overall tumor burden reduction by BOR per modified RECIST 1.1 and iBOR per modified irRC-RECIST will also be summarized. Tumor assessments occurring after the start of the first subsequent anti-cancer therapy will be excluded from the analysis of tumor burden. With the exception of tumor assessments with an increase of tumor burden $\geq 20\%$ and also demonstrate ≥ 5 mm increase from nadir, tumor assessments occurring on or after the complete or partial removal/reduction of any target lesion with melanoma on pathology evaluation or unknown pathology results will also be excluded from the analysis of tumor burden.

10. Changes From Protocol-specified Analyses

Not applicable.

11. Literature Citations / References

Brookmeyer R and Crowley J. A confidence interval for the median survival time. *Biometrics*. 1982;38:29-41.

Clopper, C. and Pearson, E. (1934) "The Use of Confidence or Fiducial Limits Illustrated in the Case of the Binomial," *Biometrika*, 26, 404–413

Eisenhauer, A., et al (2009) "New Response Evaluation in Solid Tumors: Revised RECIST Guideline (version 1.1)", *EJC*, 45, 228-247.

[figure not shown]
Lin, Guixian, Ying So, and Gordon Johnston. "Analyzing survival data with competing risks using SAS software." *SAS Global Forum*. Vol. 2102. 2012.

[figure not shown]
Pintilie, M. (2006) *Competing Risks: A Practical Perspective*. Wiley.

<http://dx.doi.org/10.1002/9780470870709>

12. Appendices

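### The primary ORR counts a response seen at a single visit, and no visible analysis gives the confirmed rate under the same criteria

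*SAP*

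**What the plan says.** SAP Section 5 defines best overall response per modified RECIST 1.1 as the best visit response up to the first PD, and adds: "Per RECIST 1.1, a confirmation of CR or PR by a consecutive subsequent tumor assessment will not be required for the derivation of BOR". The primary endpoint follows directly: "ORR is defined as the incidence of a BOR of CR or PR per modified RECIST 1.1". SAP 9.5.1 gives this rate one exact (Clopper-Pearson) 95% CI. Protocol 10.4.2.2 defines ORR in the same way, and the response matrix in Protocol Table 12-6 has no confirmation step.

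Confirmation at least 28 days later is required only under modified irRC-RECIST (SAP Table 5.1; Protocol Table 12-7). The resulting iORR also has an exact CI (SAP 9.5.2), per cohort and pooled (SAP 9.1).

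Duration of response per modified RECIST runs over "the time from the date of an initial response of CR or PR to the earlier of PD" or death, and DRR is built on it. The visible repeats of the primary analysis change the population (the per-protocol set and an optional exclusion by prior anti-PD-1 lines, SAP 9.5) or the subgroup (SAP 4.2). None changes the confirmation rule.

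**The concern.** With no control arm read under the same conditions, the primary rate has to be interpreted by itself. On the same scans, confirmed responders are a subset of those counted, so the primary rate can only equal or exceed a confirmed rate. A reader needs to know how much of it rests on one-time readings, and the visible outputs do not say.

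The label is also missing where it matters most. Both documents call the futility responder unconfirmed (Protocol 10.4.1.1, SAP 7.1). The primary-endpoint row in Protocol 10.4.2.2 and SAP 9.5.1 do not. The protocol's rationale cites a confirmed ORR of 57.1% per irRC for the same combination in the first-line setting. A reader could set the new rate beside that figure without noticing that the counting rule differs.

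**Working it through.** **1. Reproduce the plan's figure.** Inputs: 18 responders and N = 72 (SAP 3.2). The exact limits for x of n are the 0.025 quantile of Beta(x, n − x + 1) and the 0.975 quantile of Beta(x + 1, n − x). For 18/72 this gives 15.54% and 36.60%, matching the stated 15.5 and 36.6.

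**2. Remove k responses as not confirmed.** The value of k is an assumption. All 72 subjects are taken to be in the FAS and pooled.

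| k of 18 | Confirmed / N | Rate | Exact 95% CI |
|---|---|---|---|
| 0 | 18/72 | 25.0% | 15.5 to 36.6 |
| 1 | 17/72 | 23.6% | 14.4 to 35.1 |
| 2 | 16/72 | 22.2% | 13.3 to 33.6 |
| 3 | 15/72 | 20.8% | 12.2 to 32.0 |

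Each response is worth 1/72 = 1.4 points. In a 15-subject cohort it is worth 1/15 = 6.7 points: 4/15 = 26.7% (7.8 to 55.1) becomes 3/15 = 20.0% (4.3 to 48.1).

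**3. Check whether iORR already supplies the answer.** Take two hypothetical subjects, each with a baseline target sum of 100 mm.

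- Subject A has 70 mm at week 12 and 80 mm at week 24, with no new lesions, no non-target progression and no later response. Week 12 is PR (−30%). The PD threshold is 70 × 1.20 = 84 mm, so 80 mm (+14.3% from nadir, −20% from baseline) is SD. BOR is PR, and A counts in ORR. Under SAP Table 5.1 the iPR is not confirmed, iBOR is iSD, and A does not count in iORR.
- Subject B has 65 mm at weeks 12 and 24, with an unequivocal new non-measurable lesion at week 12. Under Protocol Table 12-6 that is PD at week 12, and B is not in ORR. Under Table 12-8 B is iPR at both visits, 12 × 7 = 84 days apart, and so counts in iORR. The note to that table says: "Unequivocal iPD of non-target lesions and/or the appearance of new, non-measurable lesions do not constitute overall iPD".

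Across A and B, ORR is 1/2 and iORR is 1/2. The difference is zero although the only ORR responder is unconfirmed. So iORR does remove a PR that falls back to SD, but ORR minus iORR mixes confirmation with a change of criteria.

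**4. Check DOR and DRR.** Subject A's duration starts at week 12 and does not stop at the fall to SD. If A stays free of PD long enough, A can even count as a durable responder. A PR followed by PD shows as a short duration. A PR with no later evaluable scan is censored at the response date if the subject is alive, and is an event if the subject dies. These endpoints describe how long responses last before PD or death. They do not give the proportion of subjects whose response was seen twice.

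**The case against.** The strongest reply is that nothing here is wrong. The rule is stated openly, ORR is defined consistently with it, there is no hypothesis test, and the futility rule uses unconfirmed response by design. All of that stands.

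A second reply is that persistence is already covered, because iORR, DOR, DRR and iDRR are all planned and iORR excludes subject A with a CI. This stands in part. A reader might infer that the plan has no confirmed response rate at all, or that a PR falling back to SD goes undetected. Neither is so. What is missing is a confirmed rate under the primary criteria.

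A third reply is that a repeat reading by the same investigator measures persistence and does not remove reader bias. That is correct and limits what the added analysis can show. A real but short response can also fail confirmation when scans are 12 weeks apart, so a non-confirmed response is not necessarily a false one.

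Finally, the exploratory endpoints and their SAP section are redacted, so a confirmed ORR may exist there.

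**Conclusion.** The point holds as a reporting gap: the visible plan does not show how far the primary ORR depends on single readings under its own criteria. Its size cannot be derived from the documents. The illustration of 1 to 3 of 18 responses shifts the pooled estimate by 1.4 to 4.2 points, against an interval about 21 points wide.

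Three stronger readings are not supported.

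- The ORR and iORR rules do not contradict each other. They belong to two separate sets of criteria.
- The drop of the lower limit below 15% when one of 18 responses fails is not a failed threshold. The sample-size text names that figure for N = 100, and the study is descriptive.
- Nothing shows that the primary rate is inflated, only that it cannot be lower than a confirmed rate on the same scans. Whether RECIST 1.1 itself waives confirmation in this setting cannot be checked from the documents, and no finding is made on that.

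It is a low-cost improvement to consider.

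**What to change.** Keep the primary endpoint. Call it unconfirmed ORR in SAP 9.5.1 and in its tables.

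Add to SAP Section 5 and 9.5.1 a sensitivity analysis of confirmed ORR per modified RECIST 1.1:

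- A CR or PR must be repeated at the next evaluable assessment at least 28 days later, before PD and before subsequent anticancer therapy.
- A repeat CR or PR within 28 days is ignored, as in SAP Table 5.1.
- All FAS subjects stay in the denominator.
- Exact 95% CIs are given per cohort and pooled, at the primary and final analyses.

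List the unconfirmed responders by reason: next visit SD or PD; awaiting the next scan; no further evaluable scan, including death; subsequent therapy started; or later assessments excluded after target-lesion removal. The last reason is needed because Protocol 7.1.5 says "Investigators may choose to resect lesions which become suitable for resection to render the subject free of macroscopic disease", while the SAP drops, except for PD, "overall visit response assessments occurring on or after a complete or partial removal/reduction of any target lesion" when pathology showed melanoma or was unknown. A PR followed by such a resection, with no qualifying repeat before it, can never be confirmed.

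The cost is one derived variable, one reason variable and one table row per cohort and pool, from scans already scheduled at weeks 12 and 24 and every 12 weeks after that. There are three downsides. The added rate is equal or lower. It understates responses first seen at the last scan before the 24-week cut, which is why it should be repeated at the final analysis. It reflects persistence as judged by the same reader, so it should be read together with the reason list.
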